#### **b. Safety Analyses**

Every individual complication will be evaluated by all members of the study team immediately after the event has occurred. The study team would review the case and its proceedings to determine whether the event was a direct result of the procedure or its technique, and whether this could have been prevented. The complication would also be scored for its severity based on the Clavien-Dindo Classification of Complications. If there is a severe complication, or if the complication is a direct result of the procedure or its technique, a technical pause would be called for in order to re-clarify the technical aspects as well as processes to avoid a repeat complication before the trial is resumed.

c. Interim Analyses

Interim analysis would also be carried out in a timely fashion (after 50% and 75% of the required sample size has been randomised). This would allow statistically significant differences in the outcome of the procedures to be identified. If one arm is grossly different from the other, the study team would convene to evaluate whether this outcome difference is regarded as a safety hazard to subsequent patients. If so, the trial would be halted or terminated prematurely.

d. Describe the types of statistical interim analyses, including their timing.

Interim analysis would also be carried out in a timely fashion (after 50% and 75% of the required sample size has been randomised). This would allow statistically significant differences in the outcome of the procedures to be identified. If one arm is grossly different from the other, the study team would convene to evaluate whether this outcome difference is regarded as a safety hazard to subsequent patients. If so, the trial would be halted or terminated prematurely.

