## **4.4 Discontinuation/Withdrawal**

### **4.4.1 Discontinuation Criteria**

Discontinuation criteria of the trial would either be due to:

- a. Safety issues of LAH techniques
- b. Significant number and severity of the complications
- c. Statistically overwhelming evidence that 1 method is superior over the other

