## **7.4 Safety Monitoring Plan**

The Data Safety Monitoring Plan (DSMP) for this study can be divided into individual events and collated events.

Every individual complication will be evaluated by all members of the study team immediately after the event has occurred. The study team would review the case and its proceedings to determine whether the event was a direct result of the procedure or its technique, and whether this could have been prevented. The complication would also be scored for its severity based on the Clavien-Dindo Classification of Complications. If there is a severe complication, or if the complication is a direct result of the procedure or its technique, a technical pause would be called for in order to re-clarify the technical aspects as well as processes to avoid a repeat complication before the trial is resumed.

Interim analysis would also be carried out in a timely fashion (after 50% and 75% of the required sample size has been randomised). This would allow statistically significant differences in the outcome of the procedures to be identified. If one arm is grossly different from the other, the study team would convene to evaluate whether this outcome difference is regarded as a safety hazard to subsequent patients. If so, the trial would be halted or terminated prematurely.

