### **9.2 Statistical and Analytical Plans**

#### **a. General Considerations**

All analysis would be conducted with the assistance or validation of a biostatistician. SPSS or Strata would be used to conduct the analysis. All categorical data would be analysed using the Fisher Exact Test. All continuous variables would be analysed using the Mann-Whitney U test. The level of statistical significance would be set as  $p < 0.05$ .

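### Section 4.4.1(c) allows the trial to be discontinued for superiority, but the interim passages (7.4, 9.2 c and d) describe only a safety route to a halt; the two must be reconciled

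*Protocol*

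**What the plan says.** Section 4.4.1 opens "Discontinuation criteria of the trial would either be due to" and lists three alternatives. Ground (a) is the safety of the laser technique, (b) is the number and severity of complications, and (c) is "Statistically overwhelming evidence that 1 method is superior over the other". Ground (c) is thus separate from safety.

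Sections 7.4, 9.2 c and 9.2 d give the same interim text. Looks take place after 50% and 75% of the required sample has been randomised, and "This would allow statistically significant differences in the outcome of the procedures to be identified". If the arms differ grossly, "the study team would convene to evaluate whether this outcome difference is regarded as a safety hazard to subsequent patients". The consequence follows: "If so, the trial would be halted or terminated prematurely". None of these sections mentions superiority.

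Section 9.2 a applies to the analyses in general: "The level of statistical significance would be set as" p<0.05. It also fixes the tests: "All categorical data would be analysed using the Fisher Exact Test" and "All continuous variables would be analysed using the Mann-Whitney U test". Section 9.1 sizes the trial on VAS >7.5 (50% v 25%) with 80% power, alpha below 5% and 10% loss, giving 64 per arm.

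**The concern.** One section names a superiority stop. The sections that plan the looks, which are the natural occasion for such a stop, describe a decision path that leaves it out. A study team with a clear interim difference in pain would find two different answers in its own protocol.

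Two things depend on the reading. The first is the type I error: if the only level in the document served as the superiority criterion at each look, the alpha promised in 9.1 would not hold. The second is how readily the trial stops. Under the planning assumptions an interim p<0.05 is more likely than not, whereas a strict criterion would be met in a minority of trials. A reader of an early stop would need to know which rule had applied, and this protocol does not say.

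**Working it through.** **1. The planned sample size.** Inputs from 9.1: 50% v 25%, power 80%, alpha 5%. Sidedness is not stated; two-sided is assumed because it reproduces the figure. With pooled rate 0.375:

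n = [1.960·√(2·0.375·0.625) + 0.842·√(0.5·0.5 + 0.25·0.75)]² / 0.25² = (1.342 + 0.557)² / 0.0625 ≈ 57.7, so 58 per arm.

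58 × 1.1 = 63.8, so 64, as stated (58/0.9 would give 65). This is a fixed-design figure with no allowance for interim looks.

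**2. The looks.** 50%, 75% and 100% of 64 are 32, 48 and 64 per arm, assuming that everyone randomised has VAS data. With 10% loss they are 29, 43 and 58.

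**3. VAS >7.5 with Fisher's test (exact calculation).** Begin with the product of two Binomial(32, p) distributions. At each look, add up the probability of all tables that reach the criterion, remove them, and carry the rest forward with the next 16 patients per arm. At a common rate of 37.5% with p<0.05 at every look, the cumulative error is 2.92%, 4.55%, then 6.25%.

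**4. One continuous endpoint (normal theory).** The test statistics at information 0.5, 0.75 and 1 have correlation √(tᵢ/tⱼ), that is 0.816, 0.707 and 0.866. The overall error is 1 − P(|Z| < 1.96 at all three looks) = 9.73%. Mann-Whitney simulations gave 9.5% to 9.9%.

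**5. Overall two-sided type I error (%).** Fisher columns are for common rates of 25 / 37.5 / 50%.

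| Rule (final at p<0.05) | Fisher, 32/48/64 | Fisher, 29/43/58 | One continuous endpoint |
|---|---|---|---|
| Interims at p<0.05 | 5.88 / 6.25 / 6.32 | 5.73 / 5.85 / 5.67 | 9.73 |
| Interims at p<0.01 | 3.33 / 3.78 / 3.27 | 3.46 / 3.39 / 3.60 | 5.57 |
| Interims at p<0.001 | 3.07 / 3.49 / 3.00 | 3.17 / 3.08 / 3.24 | 5.02 |
| Final test only | 3.06 / 3.48 / 2.98 | 3.16 / 3.07 / 3.23 | 5.00 |

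Over common rates from 5% to 95%, the highest Fisher value with p<0.05 at every look is 6.4% (5.9% with loss). For one continuous endpoint, interims at p<0.005 give 5.22%. If the interims serve safety only and support no superiority claim, a halt can only remove chances to reject, so the error is at most that of the final test.

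**6. How often an interim look would cross if 50% v 25% is true (Fisher).** At p<0.05: 46.0% + 21.4% = 67%. At p<0.001: 7.2% + 11.7% = 19%. With 10% loss: 63% and 15%.

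**7. Power with interims at p<0.001 against the final test only (Fisher).** 80.2% v 80.2% at 64 per arm, and 74.4% v 74.3% at 58. The lower level after loss is not caused by the interim rule.

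**The case against.** The passages can be read as complementary. Section 4.4.1 is a general list of grounds, 7.4 is a safety plan, and the interim text says that a hazard leads to a halt, not that only a hazard can. A reader might infer a flat contradiction; the wording does not go that far. But 9.2 c and d are the statistical interim sections, and they too give only the safety route, so the misalignment stands.

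A reader might also infer that the trial will stop at p<0.05 and that its error is therefore inflated. The documents do not support that. No sentence ties p<0.05 to stopping, and both 4.4.1(c) and the interim text use words that suggest a much stricter bar. For VAS >7.5 by Fisher's test, even interims at p<0.01 stay below 5%. This objection holds, and it is why the error figures are only an illustration.

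A numerical boundary is commonly left to a statistical analysis plan, which may exist. That is fair, and the absence of a boundary is not the point made here. A boundary in another document would still leave 4.4.1(c) and 9.2 c/d unaligned on whether superiority can stop the trial, and would leave 9.2 a giving one level without limiting it to the final test.

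**Conclusion.** The point holds as a misalignment within the protocol: superiority is a ground for discontinuation in 4.4.1(c) and is missing from the decision path in 7.4 and 9.2 c/d. It should be fixed.

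The effect on type I error is conditional. If p<0.05 on a single endpoint were used for a superiority claim at all three looks, the overall two-sided error would be 5.7% to 6.3% for VAS >7.5 by Fisher's test, about one point above the stated limit, and about 9.7% for one continuous endpoint. With a strict level, or with safety-only interims, it is about 5% or less.

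The 9.7% should not be read as a ceiling. It covers one endpoint, and the interim text names none. Section 2.2 gives daily VAS over 10 days, so testing several days or outcomes at each look would give more. The figures assume a two-sided test, looks at exactly 50%, 75% and 100%, and VAS data complete or reduced by 10% at each look.

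**What to change.** Reconcile 4.4.1(c) with 7.4 and 9.2 c/d in one of two ways. Neither needs a change to the safety route.

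(a) If superiority can stop the trial, state in 4.4.1(c) and 9.2 c/d that this needs a strict pre-specified level on one named endpoint, and in 9.2 a that p<0.05 applies to the final analysis only. The endpoint must be named because 2.2 gives daily VAS while 9.1 uses VAS >7.5 without a day or summary. VAS >7.5, with its day or summary stated, would fit the sample size. Two-sided p<0.001 at each interim would serve: overall error is 3.0% to 3.5% by Fisher's test and 5.0% by normal theory, with power unchanged. Other boundaries that hold 5% would do as well.

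(b) If it cannot, remove 4.4.1(c) and state in 9.2 c/d that interim comparisons serve safety review only and support no superiority claim.

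Either costs a few sentences and no extra patients. The downside of (a) is that an interim p between the strict level and 0.05 cannot be used as proof of superiority; under (b) no interim result can.

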## **10 DIRECT ACCESS TO SOURCE DATA/DOCUMENTS**

The investigator(s)/institution(s) will permit study-related monitoring, audits and/or IRB review and regulatory inspection(s), providing direct access to source data and document.

## **11 QUALITY CONTROL AND QUALITY ASSURANCE**

All data collected is prospective and the study team members and research administrators will convene to go through the peri-operative package, as well as the variables which are going to be collected for the study. This will help standardise the method of assessment and finetune the method of administering the phone-based questionnaire.

All the study co-investigators would have also completed the CITI-training workshop and would be cognisant of the need for uniformity in terms of assessment of intraoperative and post-operative variables.

## **12 ETHICAL CONSIDERATIONS**

This study will be conducted in accordance with the ethical principles that have their origin in the Declaration of Helsinki and that are consistent with the Good Clinical Practice and the applicable regulatory requirements.

This final Clinical Trial Protocol, including the final version of the Participant Information Sheet and Consent Form, must be approved in writing by the Centralised Institutional Review Board (CIRB) and regulatory approval from Health Sciences Authority (HSA), prior to enrolment of any patient into the study.

The principle investigator is responsible for informing the CIRB and HSA of any amendments to the

protocol or other study-related documents, as per local requirement.

## **12.1 Informed Consent**

Upon satisfaction of the inclusion and exclusion criteria, the primary surgeon (co-investigator) would introduce the trial to the patient in their preferred language either themselves or through a proxy. Upon interest, the research administrators will provide further details of the trial to the patient in a separate room in the clinic/wards. The patient will have ample time to read the patient information form (in the language that the patient can read) and consider enrolment into the trial. After the decision to participate, he/she would be invited to sign on the recruitment consent forms.

The research administrator and co-investigators would have to document the consult and the risks that of participation and of the techniques that were explained. In obtaining and documenting informed consent, the investigator should comply with the GCP guidelines and to the ethical principles that have their origin in the Declaration of Helsinki.

## **12.2 Confidentiality of Data and Patient Records**

Data will be entered into a data collection sheet by the study team or on the peri-operative package by the patient. All these data will be scanned in and images stored in a dedicated encrypted external hard-drive for archiving purposes. Hard-copy forms will be stored in a ring-file that is kept under lock-and-key by the PI. The data on the 2 data collection forms will be separately entered into a password-protected excel document, not having any patient identifiers, and stored in the dedicated encrypted hard-drive in a separate folder for the purposes of data analysis.

Only the study administrators and study co-investigators will have access rights for data entry and analysis through the PI.

## **13 PUBLICATIONS**

The study team owns the data and analysis. The manuscript would be written by a member of the study team and approved by the PI before presentation at an international/regional and local scientific conference.

The details of analysis would be published in a peer reviewed journal that is also registered in at least MEDLINE.

## **14 RETENTION OF TRIAL DOCUMENTS**

Records for all participants, including CRFs, all source documentation (containing evidence to study eligibility, history and physical findings, laboratory data, results of consultations, etc.) as well as IRB records and other regulatory documentation should be retained by the PI in a secure storage facility. The records should be accessible for inspection and copying by authorized authorities.

All these data will be scanned in and images stored in a dedicated encrypted external hard-drive for archiving purposes. Hard-copy forms will be stored in a ring-file that is kept under lock-and-key by the PI. The data on the 2 data collection forms will be separately entered into a password-protected excel document, not having any patient identifiers, and stored in the

dedicated encrypted hard-drive in a separate folder for the purposes of data analysis.

Only the study administrators and study co-investigators will have access rights for data entry and analysis through the PI.

## **15 FUNDING and INSURANCE**

En-Life has agreed to sponsor 40 laser probes to initiate the study. Grants will be applied to cover the remaining cost of the other 14 laser probes. En-life has agreed to loan the Laser Generator for free. Singhealth research indemnity insurance – for utility to cover for the management of any complications during the trial

# List of Attachments

## Appendix 1 Study Schedule

[figure not shown]

Figure 1. CONSORT diagram of patient involvement in COHLAH trial

## Appendix 2 Post-procedure Questionnaire Package (Attached separately)
